11.5 Study Termination

In the event that the study is discontinued, sites will immediately notify subjects to terminate study agent and return for a close-out visit to the site within 30 days.

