5.4. Per Protocol Population

The Per Protocol (PP) population will be defined as those participants in the mITT population who receive at least 80% of the assigned study treatment regimen with no substantive deviations from protocol procedures that would impact evaluation of efficacy.

A data review panel that will include the Protocol Chair ([name]) and participants from DAIT and Rho, Inc., will evaluate deviations from the protocol including, for example, violations of entry criteria, departures from assigned treatment regimen, use of prohibited therapy or HCQ prescribed outside of the study, failure to complete study visits, or to complete visits within the specified visit windows. The participant ID numbers will be replaced with randomly generated ID numbers for the PP population review.

The ARA08 study conducted an interim analysis in April 2022 as part of the regularly scheduled DSMB review. The Interim Statistical Analysis Plan is provided in Appendix 14.1. Due to the evidence of futility in the interim analysis results, the DSMB recommended that the ARA08 study stop early, and that the treatment assignments be released to the participants. Since the ARA08 study treatment assignments will be unmasked prior to database lock, the data review panel evaluation of the participants to include and exclude from the PP population will take place after the treatment assignments have been unmasked.

Levels of HCQ analyzed from serum samples taken during the study treatment period will not be used in the masked data review panel's evaluations of deviations from the protocol. The panel may exclude participants from the PP population if protocol deviations would be expected to impact the primary efficacy endpoint. Primary and secondary efficacy analyses may be replicated on the PP population.

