Population Level Summary: Estimated hazard ratios (and 95% confidence intervals) associated with the treatment effect derived from the Cox proportional hazards model.	Analysis: A Cox proportional hazards model will be fit with covariates for site (Colorado vs. other sites) and method of recruitment, along with treatment interactions. Only interaction terms with p-values<0.05 will be retained in the model. Wald chi-square tests will be used to generate p-values associated with HRs for the treatment effect. Note: The validity of the proportional hazards assumption will be evaluated.
NOTE: Originally, the method of Lee, Wei, and Amato (Lee, et al. 1992) [3] was planned to estimate HRs for the treatment effect from the marginal Cox models for clustered data under assumptions of independent and exchangeable correlation structures to account for familiar clustering. However, familial cluster was not an issue for this study, so only the traditional Cox proportional hazards model will be performed.	
Estimand Label: Secondary 5.3	
Population: mITT	IES Policy 1
Population Level Summary: Kaplan-Meier (KM) survival curves (with 95% confidence intervals) will be estimated from baseline through Month 36 for each group defined by site (Colorado vs other) and treatment arm.	Analysis: The analysis will be based on the KM survival curves for time to IA from baseline through 36 months. Survival for this analysis is defined as absence of IA. Time-to-event data are censored under the assumption of non-informative censoring. Log rank tests will be used to compare HCQ vs. placebo, and to compare the Colorado study site vs. all other study sites within each treatment arm.

8.3.5. Study Objective 6

Study Objective 6 is to explore the relationship between baseline and evolving symptoms, risk factors and the development of future CL- RA and response to HCQ. Baseline RA symptoms include self-reported joint pain, stiffness, and swelling, and overall fatigue. Risk factors include but are not limited to age, sex, genetic factors, socio-economic status, education, tobacco exposure, medications and medical hormone use, and dietary factors. The clinical endpoint to evaluate this objective will be the development of CL-RA through 36 months. Details on the derivation of the development of CL-RA are provided in section 8.2.1.

Table 13: Estimand of Study Objective 6

Variable: Time to development of CL-RA	
Estimand Label: Secondary/Exploratory 6.1	
Population: mITT	IES Policy 1

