Population Level Summary: Hazard ratios (HRs) associated with potential risk factors and modifiers to the HR for the treatment effect comparing HCQ vs. placebo will be estimated with 95% CIs based on a Cox proportional hazards model.	
Analysis: In the first step in the analysis, fixed effect characteristics of participants who developed CL-RA will be compared to those who did not develop CL-RA during the study using descriptive (e.g., means (SD) or n (%)) and inferential statistics (e.g., Mann-Whitney or Fisher-type exact statistics) appropriate for the nature of the variable.
 
In the next step, the impact of potential risk factors on the development of RA and modification of the treatment effect will be explored using a Cox proportional hazards model. To identify a subset of risk factors for possible inclusion in a final model, we will first run preliminary models each with one potential risk factor, treatment, and the treatment*risk factor interaction. Risk factors with p-values <0.1, and interaction terms with p-values <0.05 will be considered for the final model. The same criteria for inclusion will be used for the final model. Interaction terms will be evaluated first, dropping least significant terms one-by-one until only interactions with p<0.05 remain. Fixed effect components of interaction terms will be included in the final model regardless of p-value. For other fixed effect terms, least significant terms will be dropped one-by-one until only terms with p<0.1 remain. Note: The validity of the proportional hazards assumption will be evaluated.
 
Finally, if results of analyses described in Section 8.3.6, Study Objective 7 or Section 8.3.7, Study Objective 8 suggest that evolving symptoms or risk factors are potentially related to the development of CL-RA, we will consider adding time-varying covariates to the model developed above. The modeling approach will follow that outlined above. Time-varying covariates must be carefully defined prior to modeling, and models must be interpreted with caution.
 
Note: The time-varying covariate model will be exploratory and only undertaken if warranted by results of other analyses.

Fixed effects (i.e., potential risk factors) to be evaluated include:

- Study site (Colorado vs other sites)
- Method of recruitment (FDR, Population-based screening, rheumatology clinic)
- Baseline self-reported joint pain
- Baseline self-reported joint stiffness
- Baseline self-reported joint swelling

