The criteria at each interim analysis stage k to determine if the primary null hypothesis should be rejected will be determined by O'Brien-Fleming (OBF) boundary values for the standardized Z scores (Z_{OBFk}). PROC SEQDESIGN will be used to calculate the OBF boundary criteria using information levels based on the proportion of the maximum person-time accumulated on the date of data snapshot for the planned DSMB meeting. Enrollment closed on November 1, 2021 with 144 participants randomized to the study. Hence, the maximum person-years for the study is 144 participants * 3 years = 432 person-years. On the date of the data snapshot, we will compute the information fraction as the sum of time accrued from the day of randomization over all individuals divided by 432. Person-time for individuals randomized more than 3 years prior to the date of the data snapshot will be set at 3.0 person-years. In the example below, we are assuming data snapshot dates of 01FEB2022 and 01FEB2023 for the spring 2022 and spring 2023 DSMB meetings, respectively. Based on the study progress of all randomized participants, the information proportions for each interim analysis stage would be as follows:

Table 3: Estimated Information

Interim Analysis Stage (k)	Time Point	Elapsed Study Time (years)	Elapsed Study Time (person-years)	Estimated Information Proportion (I_k)
1	Spring 2022 DSMB [01FEB2022]	5.8	366.5	0.848
2	Spring 2023 DSMB [01FEB2023]	6.8	405.4	0.938
Final	End of Study [01NOV2024]	8.5	432.0	1.000

Note the actual information proportions will vary depending on the information available on the dates of data cuts.

At each interim analysis stage k , the primary hypothesis will be tested as follows:

- If $X_{5k}^2 \geq (Z_{OBFk})^2$, the null hypothesis H_0 that the RA-free survival at 3 years (36 months) is equal across arms is rejected, indicating there is strong evidence of a treatment effect.
- If $X_{5k}^2 < (Z_{OBFk})^2$, the null hypothesis H_0 that the RA-free survival at 3 years (36 months) is equal across arms is not rejected.

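### Objective 6, step one, tests risk factors on an ever/never CL-RA split that ignores censoring; the effect is confined to its unadjusted p-values

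*SAP*

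**What the plan says.** SAP 8.3.5 sets the horizon for Objective 6: "The clinical endpoint to evaluate this objective will be the development of CL-RA through 36 months". Table 13 names the outcome as "Variable: Time to development of CL-RA", applies IES Policy 1 in the mITT population, and gives Cox hazard ratios as the population-level summary.

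The analysis cell then has several steps. In the first, "characteristics of participants who developed CL-RA will be compared to those who did not develop CL-RA during the study", using descriptive statistics and "inferential statistics (e.g., Mann-Whitney or Fisher-type exact statistics) appropriate for the nature of the variable". No minimum follow-up, at-risk restriction or rule for censored participants is given. The second step fits a Cox model for each factor with treatment and their interaction. The p-values from those models decide what is considered for the final model.

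SAP 5.4 reports that "the DSMB recommended that the ARA08 study stop early, and that the treatment assignments be released to the participants". Protocol 11.5 asks participants, if the study is discontinued, to "return for a close-out visit to the site within 30 days". On accrual, Interim SAP 5.2.2.1 (SAP Appendix 14.1) says: "Enrollment closed on November 1, 2021 with 144 participants randomized to the study".

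**The concern.** A two-way split has no place for a censored participant. Someone observed for a few months without CL-RA has the same weight as someone examined at Month 36. Three groups enter the non-cases this way:

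- participants cut off by the early stop;
- participants who dropped out;
- participants censored under IES Policy 1 for prohibited medication. These include people treated for RA diagnosed outside the study, unless on-study data meet the endpoint.

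If follow-up length is unrelated to a factor, the step-one test stays valid under the null and only loses power. If the factor's prevalence changed over accrual, or it relates to dropout, follow-up length becomes a confounder. Drift is plausible: enrolment was projected at about 24 months (Protocol 3.1), while Interim SAP Appendix 8.1 assumes 5.5 years. Site and recruitment method are both on the factor list, and minimization balanced them between arms, not over calendar time. A reader could then see two sets of unadjusted p-values for about 30 factors that disagree for reasons unrelated to risk.

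**Working it through.** **Inputs from the documents.** Interim SAP 5.2.2.1 and Table 3: 144 randomized, maximum 144 × 3 = 432 person-years, 366.5 accrued at 01FEB2022, 405.4 projected at 01FEB2023. Interim SAP Appendix 8.1: 20% attrition per arm. Protocol 8.1: 3-year risks of 50% and 25%.

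**Reproducing the plan's figures.** 366.5/432 = 0.848 and 405.4/432 = 0.938, as in Table 3. A Wald test on logit 3-year survival with 80 per arm gives power 0.896, against the stated 90%.

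**Bounds from document figures only.** Between the two dates 405.4 − 366.5 = 38.9 person-years remained to accrue. One participant can add at most 1 year, so at least 39 of 144 (27%) had not reached 36 months since randomization at 01FEB2022. Had follow-up run to 01FEB2023, 432 − 405.4 = 26.6 person-years would be missing. The last enrollee (1 November 2021) would lack 1.75 years, and 26.6/1.75 = 15.2, so at least 16 participants would be short. Both counts include anyone already diagnosed.

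**Estimate.** Let B be those with 2–3 years at 01FEB2022 and C those with 0.25–2 years, with uniform enrolment within each band.

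- Gain over the next year: 0.5B + C = 38.9
- Shortfall at 01FEB2022: 0.5B + 1.875C = 65.5
- Solution: C = 26.6/0.875 = 30.4 and B = 17.0, about 47 participants (33%).

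**Simulated composition of the step-one groups.** Assumptions: 72 per arm, exponential CL-RA times, exponential loss of 20% over 3 years, follow-up ending early April 2022, the enrolment pattern above, 4,000 runs per scenario. Full follow-up means reaching Month 36 within its 14-day window.

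| 3-year risk (placebo/HCQ) | Non-cases | Of these, under 36 months | True 3-year cases called non-cases | Crude vs KM risk |
|---|---|---|---|---|
| 50%/25% | 100 | 50 (50%) | 11 of 54 | 30% vs 38% |
| 50%/50% | 86 | 45 (53%) | 14 of 72 | 41% vs 50% |
| 30%/30% | 110 | 53 (48%) | 9 of 43 | 24% vs 30% |
| 50%/25%, no early stop | 95 | 23 (24%) | 5 of 54 | 34% vs 37% |

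**Simulated rejection rates at two-sided 0.05.** Prevalence is given for early/late enrollees, where late means under 36 months at 01FEB2022. HR-2 rows use 50%/25% as the risk without the factor; null rows span the risk scenarios run.

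| Factor | Fisher, ever/never | Log-rank |
|---|---|---|
| Null, no drift (40%/40%) | 3.6–4.3% | 4.5–5.1% |
| Null, 30%/60% | 5.1–5.9% | 4.5–5.5% |
| Null, 20%/70% | 8.9–11.0% | 5.6–5.9% |
| HR 2, no drift | 60% | 69% |
| HR 2, 30%/60% | 41% | 68% |
| HR 2, 60%/30% (reversed) | 76% | 69% |

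A separate simulation with 96 early and 48 late enrollees gave 61% against 69% with no drift, 43% against 68% at 30%/60%, and null rejection of 8–12% at 20%/80%. A repeat of the 20%/80% case on the settings above gave 10–14%. The reversed-drift row depends on how baseline risk is set: another run gave 66% against 57%. Fisher's test rejects more often than the log-rank test in both.

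**The case against.** The strongest reply is that step one decides nothing. Entry to the final model rests on the preliminary Cox models, and the reported hazard ratios come from Cox models that handle censoring. The estimand is labelled Secondary/Exploratory, and SAP 8.1.4 treats secondary p-values as descriptive. Site and recruitment method are also analysed with censoring in Secondary 4.2, and site again in 4.3. All of this stands and limits the severity.

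A reader might infer that the Objective 6 hazard ratios or factor selection are distorted. The documents do not support that, because no step-one p-value enters either.

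A reader might also infer that step one always hides true factors or generally inflates false positives. Neither follows. Reversed drift strengthens the apparent association, and type I error stays near nominal (5–6%) at 30%/60% drift and below 5% with none.

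Nor is step one the only place where the SAP splits participants by CL-RA status. Objectives 7 and 8 and the endpoints in 8.4 do so as well. Step one stands apart only among analyses with CL-RA as the outcome.

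Finally, the documents give no last-visit date, observed dropout or change in any factor's prevalence. SAP 5.4 reports a DSMB recommendation, which under Interim SAP section 1 goes to a further panel. The simulated figures therefore rest on assumptions; the bounds of 39 and 16 do not need them.

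**Conclusion.** The point holds at low severity. Step one applies tests that ignore censoring to an outcome its own table defines as a time to event under IES Policy 1.

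The document-based size is at least 39 of 144 participants short of 36 months since randomization at 01FEB2022, including any already diagnosed. Under 20% attrition and closure in spring 2022, about half of the non-cases lack 36 months of observation. Even without an early stop it would be about a quarter.

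The consequence is confined to the unadjusted step-one p-values:

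- about 8 points of power lost for an HR-2 factor unrelated to enrolment date (8 in one simulation, 9 in the other);
- bias in either direction if prevalence drifts over accrual;
- false-positive rates of about 8–14% only under strong drift such as 20%/80%, and about 5–6% at 30%/60%.

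**What to change.** In Table 13, make step one descriptive. Keep the table of participants with and without CL-RA, and add follow-up time per group and the number of non-cases observed for under 36 months. Remove the Mann-Whitney and Fisher-type tests. Take each factor's unadjusted p-value and HR from a log-rank test or a Cox model with treatment and the factor, using the censoring of Primary 1.0.

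The cost is a wording change and little programming. Step two already fits a Cox model for every listed factor with treatment and the interaction, so the version without the interaction is a small addition. No new data are needed.

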Site coordinators will call subjects at Week 18, 30, and 42 and at Month 15, 21, 27, and 33 to answer subject questions, update contact information, and to assess AEs/reactions, study drug dosing and pregnancy status (during the treatment period), and joint symptoms. If a subject indicates that he/she is experiencing joint symptoms suggestive of RA (that include new or worsening joint pain, stiffness or swelling since the prior study visit), or symptoms suggestive of an AE, the subject will be asked to return to the study site as soon as possible.

Visits and assessments for subjects who develop RA, IA with erosions, or who become pregnant prior to the Month 36 visits will be different from subjects who never develop RA. Details of these assessments may be found in protocol sections 6.5.9, *Evaluations Triggered by a Swollen Joint*, 6.5.10, *Procedures for Subjects Diagnosed with Inflammatory Arthritis or Rheumatoid Arthritis by an Outside Physician*, and 6.5.11, *Special Considerations for Pregnant Subjects*.

Endpoints:

The primary efficacy endpoint is the development of clinically-apparent RA by 36 months, where clinically-apparent RA is defined in Section 2.1, *Primary Objective*.

Secondary efficacy and safety endpoints are described in Sections 3.3.1, *Secondary Efficacy Endpoints*, and 3.3.2, *Secondary Safety Endpoints*.

Sample Size: 200 eligible subjects will be randomized in a 1:1 ratio.

Data Analyses: For the primary analysis, we are interested in demonstrating a long-term impact of a 1-year course of HCQ treatment on preventing the development of clinically-apparent RA (defined in Section 2.1, *Primary Objective*) in high-risk subjects. As such, rather than comparing full survival curves between treatment arms, the sample size for this study was selected to achieve sufficient power to compare survival curves at a fixed point 3 years after initiating treatment with HCQ.

All secondary analyses will be conducted in an exploratory fashion with p-values and confidence intervals presented as descriptive statistics with no adjustments for multiple comparisons. Tests will be two-sided and interval estimates will be generated at the 95% confidence level.

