- Baseline self-reported fatigue
- Baseline CDAI
- Baseline SDAI
- Baseline RAPID-3
- Baseline DAS28-CRP

Autoimmunity Centers of Excellence
Statistical Analysis Plan – ARA08 StopRA

- Baseline PROMIS Profile 29 Physical Health Score
- Baseline PROMIS Profile 29 Mental Health Score
- Baseline PROMIS Profile 29 Social Health Score
- Baseline Anti-CCP3 (units)
- Baseline Anti-CCP3 Positivity (Negative (< Upper Limit of Normal (ULN), Low Positive (1.0 - <2.0 x ULN), Medium Positive (2.0 - <3.0 x ULN), High Positive (\geq 3.0 x ULN))
- Baseline IgM-RF (U/mL)
- Baseline IgM-RF Positivity (Negative (< Upper Limit of Normal (ULN), Low Positive (1.0 - <2.0 x ULN), Medium Positive (2.0 - <3.0 x ULN), High Positive (\geq 3.0 x ULN))
- Baseline hs-CRP (mg/L)
- Baseline hs-CRP Positivity (\leq 3.0 mg/L, $>$ 3.0 mg/L)
- Baseline age (years)
- Sex (male/female)
- BMI
- Baseline Shared Epitope (SE) Positivity (Yes, No)
- Baseline Shared Epitope Number of Positive Results (0, 1, 2)
- Participant has a FDR with RA (Yes, No)
- Salary level (< \$50,000; \$50,000 - < \$75,000; \geq \$75,000)
- Highest education level achieved (up to High School/GED, College, Graduate School)
- Tobacco exposure
 - Smoking status (Never smoked, Former smoker, Current smoker)
 - Baseline Pack Years at Current Level for Smokers
 - Years as Adult Living with Smoker
- Baseline Medications
 - Statin use (Yes/No)
 - Medical hormones (Yes/No)

Each fixed effect will be evaluated for its impact on the time to development of CL-RA by fitting a Cox proportional hazards model with independent variables for treatment arm, risk factor and treatment arm * risk factor interaction. The risk factors with significant p-values for the Wald chi-square test statistic, along with significant interaction terms, will be included in the final Cox proportional hazards model.

8.3.6. Study Objective 7

Study Objective 7 is to evaluate the relationship between treatment with HCQ and amelioration of symptoms of RA, and potential delay in onset of symptoms. RA symptoms include self-reported joint pain, stiffness, and swelling, and overall fatigue. The clinical endpoint to evaluate this objective will be the self-reported joint symptom counts assessed at each clinic visit.

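### Objective 6 screens each risk factor on a p-value from a model that still holds the treatment interaction, with no treatment coding stated; under 0/1 coding the reference arm decides which factors pass.

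*SAP*

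**What the plan says.** SAP 8.3.5 (Study Objective 6, Table 13) sets out three stages.

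1. Participants with and without CL-RA are compared on each characteristic by descriptive statistics and Mann-Whitney or Fisher-type tests.
2. One-factor Cox models are fitted: "we will first run preliminary models each with one potential risk factor, treatment, and the treatment*risk factor interaction". The selection rule is "Risk factors with p-values <0.1, and interaction terms with p-values <0.05 will be considered for the final model".
3. In the final model, backward elimination starts with the interactions: "Interaction terms will be evaluated first, dropping least significant terms one-by-one until only interactions with p<0.05 remain". The remaining factors are then held to p<0.1.

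The text after the list of fixed effects repeats stage 2 as "fitting a Cox proportional hazards model with independent variables for treatment arm, risk factor and treatment arm * risk factor interaction", and continues: "The risk factors with significant p-values for the Wald chi-square test statistic, along with significant interaction terms, will be included in the final" model. Here the threshold is simply significance, without the 0.1.

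The planned output is hazard ratios for the risk factors, and "modifiers to the HR for the treatment effect comparing HCQ vs. placebo will be estimated with 95% CIs". Nothing in the section states how treatment is coded or which arm is the reference. Nothing asks for an averaged or joint test of the factor, and no step removes a non-significant interaction from a preliminary model before the factor's p-value is read.

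**The concern.** Once a model contains a factor, treatment and their product, the coefficient on the factor alone is its effect where the treatment variable equals zero. What that means depends on the coding. With 0/1 coding it is the factor's effect in the reference arm, and the other arm's events contribute almost nothing to its test. Swapping the reference arm leaves the fit and the interaction p-value unchanged but gives a different factor p-value.

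Objective 6 asks which baseline features predict CL-RA. A factor that acts equally in both arms should be tested on all the events. As written, it may be tested on one arm's events and dropped before the final model, and the SAP has no step that brings it back. Two analysts could follow the text faithfully and carry different factors forward.

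**Working it through.** **Inputs**
- 144 randomized (Interim SAP in SAP Appendix 14.1, section 5.2.2.1: "Enrollment closed on November 1, 2021 with 144 participants randomized to the study"); 72 per arm assumed from 1:1 allocation.
- Exponential failure with 3-year risks of 50% and 25% (Protocol 8.1): λ = −ln(0.50)/3 = 0.231 for placebo and −ln(0.75)/3 = 0.096 for HCQ.
- 20% loss per arm (Interim SAP, Appendix 8.1), taken as exponential: c = −ln(0.80)/3 = 0.074.
- Assumed, not in the documents: a Normal factor with hazard ratio 1.5 per SD in both arms; as a second case, a binary factor with 50% prevalence and hazard ratio 2 in both arms.

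**1. Background check.** The documents give no power for this screen. The protocol's primary-test figures (80 per arm) reproduce: 91.0% against 90% stated, 4.8% against 4.6% under the null, 81.1% against 81%, and 77.2% against 77%.

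**2. What is tested.** Write log hazard = baseline + βT·T + βF·F + βI·T·F. The coefficient on F is:
- placebo = 0: βF, the placebo-arm effect;
- HCQ = 0: βF + βI, the HCQ-arm effect;
- ±1/2 coding: βF + βI/2, the equally weighted average.

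The interaction p-value is the same in all three.

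**3. Events by arm.** P(event) = λ/(λ+c) × [1 − exp(−3(λ+c))].
- Placebo: 0.756 × (1 − 0.50×0.80) = 0.454; × 72 = 32.7.
- HCQ: 0.563 × (1 − 0.75×0.80) = 0.225; × 72 = 16.2.

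Placebo therefore holds 32.7/48.9 = 67% of events. The simulation with the Normal factor averaged 33.4 and 17.1.

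**4. Approximate pass rate at two-sided 0.10.** Φ(√D × ln 1.5 − 1.645), with ln 1.5 = 0.405.
- Placebo arm, D = 33.4: Φ(2.34 − 1.645) = 76%.
- HCQ arm, D = 17.1: Φ(1.68 − 1.645) = 51%.
- All events, D = 50.5: Φ(2.88 − 1.645) = 89%.
- Arm average: SE = ½√(1/33.4 + 1/17.1) = 0.149; Φ(0.405/0.149 − 1.645) = 86%.

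**5. Simulation.** Each trial is fitted with the SAP's three-term model, and again without the product term. The middle column uses 3,000 trials; the last is a separate run under the same assumptions that also admits a factor when its interaction p<0.05, as the SAP does. Simulation error is about one point, √(0.5×0.5/3000) = 0.9%.

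| Source of the factor p-value | Factor p<0.1 alone | Counting interaction entry |
|---|---|---|
| Three-term, placebo reference | 75.7% | 76% |
| Three-term, HCQ reference | 51.6% | 55% |
| Three-term, ±1/2 coding | 84.1% | 86% |
| Interaction dropped if p≥0.05 (middle column: always dropped) | 88.2% | 89% |

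The two reference choices disagree on the same data in 48% of trials on the factor p-value alone, and in about 43% counting interaction entry.

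**6. Other cases.**
- Binary factor, hazard ratio 2 in both arms (factor p alone): 61%, 36%, 71% and 76% in the same row order; disagreement 52%, or 48% counting interaction entry.
- Binary factor with no effect: every version passes about 9–10%, yet the two reference choices disagree in 17.6% of trials (13.5% counting interaction entry).
- One simulated data set: factor p = 0.028 (placebo reference), 0.67 (HCQ reference), 0.092 (±1/2) and 0.042 (no interaction), with interaction p = 0.31 throughout.

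**The case against.** **The analysis is exploratory.** SAP section 3 says "All secondary analyses will be conducted in an exploratory fashion with p-values and confidence intervals presented as descriptive statistics", and the estimand is labelled Secondary/Exploratory. That stands, and it limits the consequence. It does not make the screen a good one, since identifying predictors is the purpose of this objective.

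**The one-arm test is not in the SAP.** A reader might infer that the plan tests each factor in one arm only. The documents do not support that: it follows only under 0/1 coding. Under ±1/2 coding the same model averages the arms, does not change when they are swapped, and loses only about 3 points (86% against 89%).

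**Placebo is the natural reference.** The contrast is HCQ versus placebo, which points that way but is not a coding rule. If placebo is the reference, a reader should not conclude that half the information is lost: under the design hazards about two thirds of events are in that arm, and the loss is from 89% to 76%.

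**There is a second way in.** Interaction p<0.05 also admits a factor, so a claim that the decision flips in half of trials overstates the Normal-factor case. It is about 43% once that route is counted.

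**Other stages pool the arms.** Stage 1 is not split by arm, and in the final model a factor whose interaction has been dropped is tested across both arms. A common predictor missed by the screen would therefore still appear in the stage 1 comparison. But stage 1 is not the selection rule, and the final model sees only factors that passed.

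**Pooling has a price.** Objective 6 also concerns response to HCQ, so arm-specific predictors matter. A factor acting only on placebo (hazard ratio 1.5 per SD) passes about 74% of the time with placebo as reference and about 69% under the refit rule, counting interaction entry in both. That cost is real and small. For a binary factor acting only on HCQ (hazard ratio 2), the factor p-value alone passes 10.6% with placebo as reference and 21.4% without the interaction.

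**Conclusion.** The point holds in this form: the factor p-value used for screening comes from a model that contains the interaction, the treatment coding is unstated, and the result depends on it. Under reference coding the screen tests the factor in the reference arm alone. For a factor acting equally in both arms, the pass rate falls from about 89% to 76% (placebo reference) or 55% (HCQ reference), and the reference choice changes the decision in about 43% of trials. With ±1/2 coding the loss is small.

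These figures assume 72 per arm, the design hazards, 20% exponential loss, full 3-year follow-up otherwise, and the stated factor effect. The trial stopped early for futility (SAP 5.4), so actual events may be fewer and more evenly split. If one third of participants had truncated follow-up (an assumption; the documents give no figure), disagreement counting interaction entry is 47% under the design hazards and 36% with 50% risk in both arms.

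The effect is confined to the exploratory Objective 6 screen. A reader might infer that the whole list of predictors turns on the coding; the pooled stage 1 comparison, the interaction route and the final-model elimination mean that it does not. The primary analysis does not use this screen.

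**What to change.** In SAP 8.3.5, change Table 13 and the text after the factor list as follows:

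- From the three-term model, read only the interaction p-value.
- If it is 0.05 or above, drop the product term, refit treatment plus factor, and apply p<0.1 to the factor in that model.
- If it is below 0.05, carry the factor and its interaction forward.
- Replace the unspecified significance criterion in the later text with p<0.1, so that it agrees with Table 13.
- State the treatment coding. If the three-term model is kept as the source of the factor p-value, specifying ±1/2 coding alone would recover most of the loss.

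The cost is a wording change and one extra Cox fit per factor, with no new data. The one statistical price is the slightly lower pass rate for placebo-only factors given above.
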